#### 8.4.3. Adverse events by MedDRA SOC and MedDRA PT

For all AEs, a descriptive analysis will be provided by MedDRA SOC and MedDRA PT, by randomization arm and overall. All AEs collected in the eCRF will be used for the analysis. The following template will be used.

System Organ Class / Preferred Term	Group of treatment								
	RGn550 5Hz N=xx			RGn550 10Hz N=xx			Total N=xx		
	Nb Med Hist	Nb pat	% pat	Nb Med Hist	Nb pat	% pat	Nb Med Hist	Nb pat	% pat
ANY ADVERSE EVENT	13	11	7.0	18	15	9.5	31	26	8.3
Infections and infestations	7	7	4.5	12	10	6.3	19	17	5.4
- Bronchitis	2	2	1.3	4	4	2.5	6	6	1.9
- Gastroenteritis	1	1	0.6	.	.	.	1	1	0.3
- Influenza	1	1	0.6	.	.	.	1	1	0.3
- Laryngitis	1	1	0.6	.	.	.	1	1	0.3
Gastrointestinal disorders	3	3	1.9	.	.	.	3	3	1.0
- Gastrooesophageal reflux disease	2	2	1.3	.	.	.	2	2	0.6
- Inguinal hernia	1	1	0.6	.	.	.	1	1	0.3

#### 8.4.4. Adverse device events by MedDRA SOC and MedDRA PT

For all ADEs, a descriptive analysis will be provided by MedDRA SOC and MedDRA PT, by randomization arm and overall.

For all ADEs occurring during the first session (at D0), a descriptive analysis will be provided by MedDRA SOC and MedDRA PT, by randomization arm and overall.

For all ADEs occurring during the second session (at D7), a descriptive analysis will be provided by MedDRA SOC and MedDRA PT, by randomization arm and overall.

The same template as above (i.e. for Adverse events) will be used.

## 8.5. Efficacy analysis

### 8.5.1. Analysis of the secondary performance endpoints

The secondary performance endpoints will be analyzed in the FAS population by treatment groups, excluding data that would be collected after the following intercurrent event: treatment group switch during follow-up.

#### 8.5.1.1. Automated oculomotor and oculopostural functions and balance function

For the evolution of parameters of oculomotor and oculopostural functions and balance function defined in Section 0, the following timepoints will be compared: (D0 after treatment - D0 before treatment, D7 before treatment - D0 before treatment, D7 after treatment - D0 before treatment, and D52 – D0 before treatment). A mixed effect regression model (logistic model for a categorical parameters and a linear model for continuous parameters) will be used with a patient random effect. Group effects (5 Hz vs 10Hz), period effects (D0 before, D0 after, D7 before, D7 after and D52) and the group-by-period interaction will be added as fixed effects. The stratification variable gender (male/female) will be added in the model as covariates.

Note: the stratification variable concussion history within 6 months prior to inclusion (yes/no) will not be added in the model as too few patients had concussion history (cf. data review minutes of 18/07/2023).

The following template will be used for continuous parameters.

	Group of treatment		
Ref = D0 before treatment	RGn550 5Hz N=xx	RGn550 10Hz N=xx	Difference
Endpoint XXX at D0 after treatment			
Adjusted mean	x.xx	x.xx	x.xx
95% CI	x.xx ; x.xx	x.xx ; x.xx	x.xx ; x.xx
p-value	.	.	0.xxx
Endpoint XXX at D7 before treatment			
Adjusted mean	x.xx	x.xx	x.xx
95% CI	x.xx ; x.xx	x.xx ; x.xx	x.xx ; x.xx
p-value	.	.	0.xxx
Endpoint XXX at D7 after treatment			
Adjusted mean	x.xx	x.xx	x.xx
95% CI	x.xx ; x.xx	x.xx ; x.xx	x.xx ; x.xx
p-value	.	.	0.xxx
Endpoint XXX at D52			

		Group of treatment		
Ref = D0 before treatment		RGn550 5Hz N=xx	RGn550 10Hz N=xx	Difference
Adjusted mean		x.xx	x.xx	x.xx
95% CI		x.xx ; x.xx	x.xx ; x.xx	x.xx ; x.xx
p-value		.	.	0.xxx

From an mixed model including treatment (p=0.xxx), visit (p=0.xxx), treatment-by-visit interaction (p=0.xxxx) as fixed effects and variable xxx as random effect, variableyyy (p=0.xxx) as baseline covariate.

The following template will be used for categorical parameters.

	RGn550 10Hz vs RGn550 5Hz at visit 1	RGn550 10Hz vs RGn550 5Hz at visit 2	visit 2 vs visit 1 at RGn550 10Hz	visit 2 vs visit 1 at RGn550 5Hz
Endpoint XXX				
Odds ratio	X.X	X.X	X.X	X.X
95% CI	[X.X ; X.X]	[X.X ; X.X]	[X.X ; X.X]	[X.X ; X.X]

From an mixed model including treatment (p=0.xxx), visit (p=0.xxx), treatment-by-visit interaction (p=0.xxxx) as fixed effects, variable xxx as random effect and variableyyy (p=0.xxx) as baseline covariate.

In addition, the following analyses will be performed for exploratory purpose:

- The NPC measurement will also be analyzed in the subgroup “NPC > 5 at D0 before treatment”.
- The Maddox rod horizontal will also be analyzed in the subgroup “Horizontal deviation at D0 before treatment”.
- The Maddox rod vertical - left eye will also be analyzed in the subgroup “Vertical deviation at D0 before treatment”
- The Maddox rod vertical - both eyes will also be analyzed in the subgroup “Vertical deviation at least one eye at D0 before treatment”.

Note: the Maddox rod vertical – right eye will not be analyzed in the subgroup “Vertical deviation at D0 before treatment” as too few patients were included in this subgroup (cf. data review minutes document of 18/07/2023).

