9.5.3. Conduct

9.5.3.1. Patient Inclusion

It is planned to include 50 patients in this investigation (refer to section 9.6.1 for sample size justification).

Based on this number and considering that the site estimated that it would be able to include approximately 3 patients per week, a 4-month inclusion period is planned: from September 2022 to December 2022.

The recruited site will be the Hôpital européen Georges-Pompidou located in Paris. The principal investigator will be a neurologist specialized in sport concussions and the coinvestigator will be a sport physician and posturologist.

In current clinical practice, following a shock, a sportsperson with obvious signs of concussion is examined by a physician within 72 hours after the shock to establish the diagnosis of concussion. For example, in the context of professional rugby, the French federation's regulation requires to follow HIA protocol immediately after the shock and the appearance of such signs. This protocol, composed of three steps, is performed by a physician within 48 hours after the shock:

- Step 1: Assessment during the match using HIA1
- Step 2: Post-match assessment, the same day, using HIA2
- Step 3: 36-48 hours post-injury assessment using HIA3.

The subjects of RGnCON investigation will be identified among sportspersons examined by the principal investigator within 72 hours after the shock. They will be included if they meet eligibility criteria and agree to participate in the investigation. Of note, HIA3 is mentioned in the eligibility criteria as the diagnostic tool for concussion. Indeed, as the principal investigator is the referring neurologist for a lot of rugby clubs and several sports federations, it is expected that most subjects will be professional rugby players for whom this protocol is implemented in current clinical practice. Nevertheless, subjects practicing other sports may be included as well if they have a diagnosis of concussion confirmed by the HIA3, meet the eligibility criteria and agree to participate.

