Following this, the patient will evaluate his/her symptoms using the **SCAT5 symptom evaluation tool**. The patient will rate the intensity of every symptom from 0 (none) to 6 (severe) using a form. This will allow to calculate the total number of symptoms (out of 22) and the symptom severity score (out of 132) (see Appendix 12.3).

A **blood sample** will also be obtained from the patients by a nurse. The blood sample analysis will be performed by Montpellier Neuroscience Institute (*Institut de Neuroscience de Montpellier*) following the institute standard practice.

During the visit, the patients will be **randomized** in a 1:1 ratio to the 5 Hz group or 10 Hz group using the centralized Interactive Web Response System (IWRS) incorporated into the eCRF. A block randomization method will be used. Only patients will be blinded to their assigned treatment.

Depending on their assigned group, the patients will then be **treated** with one of the 5 Hz RGn550 devices or one of the 10 Hz RGn550 devices for 20 min. To perform the treatment, the principal investigator will follow the below instructions:

- Make the patient comfortable.
- Install the helmet on the patient's head, taking care not to bump it with the modules.
- Lightly tighten the soft helmet holding wire and check the positions of the modules. Each module can be moved slightly to adjust its position.
- On the control unit, in the menu on the left, choose the option 'Program' and choose the proposed treatment
- Finally press the red arrow to start the treatment.

A countdown is displayed on the screen indicating the time remaining until the end of the treatment session. At each treatment session, the principal investigator will fulfil a treatment sheet associated with the used device and mention the number of the treated patient, date of treatment, number of

treatment session and duration of treatment. To stop the treatment, the principal investigator will press the red button with a cross inside that is displayed on the screen (a confirmation message will be displayed to avoid any manipulation error).

Following treatment, the investigators will:

- **Perform the following tests** following the methodology described above:
 - NPC
 - Cover test
 - Maddox rod test
 - Static stabilometric test
- **Collect any AEs and DDs** that occurred during the visit.

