9.6. Statistical Considerations

9.6.1. Sample Size Justification

For a sample size of 50 patients, the probability of observing at least one ADE will be 0.87 considering a probability of ADE of 0.04. The sample size calculation was performed with SAS® v9.4.

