9.6.3. Statistical Analysis

Full details related to statistical analysis will be provided in the Statistical Analysis Plan.

The statistical analysis will be performed using SAS® Viya v9.4 (or a more recent version).

The global significance level (type I error rate) will be set at $\alpha = 0.05$ (two-sided). Adjustment for multiplicity is not applicable for the primary endpoint and no adjustment for multiplicity is planned for secondary endpoints.

Continuous data will be described by the number of missing data, number of data analyzed, mean, standard deviation, median, Q1, Q3, minimum, maximum.

Categorical data will be described by the number of missing data, frequencies and percentages of patients in each modality. The percentage of patients will be calculated once missing data are excluded from the denominator.

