### 8.5.1.2. Executive function (TMT A&B)

For the evolution of executive functions defined in Section 0, the following timepoints will be compared: (D0 before treatment – D7 after treatment) and a mixed effect regression model (logistic model for a categorical parameter and a linear model for continuous parameter) will be used with a patient random effect. Group effects (5 Hz vs 10Hz), period effects and group-by-period interaction will be added as fixed effects. The stratification variable gender (male/female) will be added in the model as covariates.

The same template as above (i.e. for continuous parameters) will be used.

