### 8.5.1.3. Concussion syndrome symptoms (SCAT5)

For concussion syndrome symptoms (SCAT5) functions defined in Section 0, the following timepoints will be analyzed (D0 before treatment, D7 before treatment, D14 and D52), a mixed linear regression model will be used with a patient random effect. Group effects (5 Hz vs 10Hz), period effects and

group-by-period interaction will be added as fixed effects. The stratification variables and SCAT5 baseline will be added in the model as covariates.

The same template as above will be used.

In addition, for exploratory purpose, the concussion syndrome symptoms (SCAT5) will also be analyzed in the subgroup “Number of previous concussions”.

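### The 5 Hz versus 10 Hz comparisons of balance, NPC and TMT are raw differences in change from D0, which is valid but less precise than adjusting for the D0 value

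*SAP*

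**What the plan says.** SAP 8.5.1.1 covers the oculomotor and balance endpoints. Its fixed effects are "Group effects (5 Hz vs 10Hz), period effects (D0 before, D0 after, D7 before, D7 after and D52) and the group-by-period interaction", with a patient random effect. D0 before treatment is thus one of five response levels, and the arms may differ there freely. On covariates it says: "The stratification variable gender (male/female) will be added in the model as covariates". The template for continuous endpoints shows a between-arm difference and p-value at each later visit, with D0 before treatment as reference. Its footnote has a slot for a baseline covariate, filled only by the placeholder `variableyyy`.

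SAP 8.5.1.2 uses the same structure for TMT with two time points, D0 before and D7 after treatment: "Group effects (5 Hz vs 10Hz), period effects and group-by-period interaction will be added as fixed effects". Gender is again the only named covariate.

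SCAT5 is treated differently. SAP 8.5.1.3 lists D0 among the analysed time points and adds: "The stratification variables and SCAT5 baseline will be added in the model as covariates".

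Protocol 9.6.3.2 specifies the same models, without the SCAT5 baseline covariate. Protocol 9.2.3 gives the choice between the two frequencies, on safety and performance, as the reason for having two arms.

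**The concern.** Randomisation makes the D0 means of the two arms equal in expectation, and the model does not use this. With near-complete data and a patient random intercept, the group-by-period contrast reduces to the difference between arms in mean change from D0. A chance difference at D0 then enters the estimate with full weight. Baseline adjustment would weight it by the regression slope of the later value on the D0 value.

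At stake is the precision of the frequency comparison, with about 25 patients per arm. The schedule of procedures already places balance, NPC and TMT at D0 before treatment, so adjustment needs no new measurement.

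**Working it through.** **Inputs from the documents.** Protocol 9.5.3.1: "It is planned to include 50 patients in this investigation". Protocol 9.5.5.1: randomisation "in a 1:1 ratio to the 5 Hz group or 10 Hz group", so n = 25 per arm. Protocol 9.6.3: alpha 0.05, two-sided. SAP 8.4.1: loss to follow-up 0% at data review.

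**Assumptions.** Rho is not given, so 0.3 to 0.9 is used. The SD s is taken as equal at all visits and data as complete.

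**The plan's own figure.** Protocol 9.6.1 states that "the probability of observing at least one ADE will be 0.87 considering a probability of ADE of 0.04". Check: 1 − 0.96^50 = 0.8701, which agrees. This is the only design calculation and concerns safety. It says nothing about the precision of the performance models.

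**Formulas.**
- SAP contrast (difference in change): variance = 2s²(1 − rho) × 2/n.
- Adjusted for the D0 value: variance = s²(1 − rho²) × 2/n.
- Ratio: (1 − rho²) / [2(1 − rho)] = (1 + rho)/2.

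Example at rho 0.5, in SD units: √(2 × 0.5 × 2/25) = √0.08 = 0.283 against √(0.75 × 2/25) = √0.06 = 0.245.

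| rho | SE, SAP | SE, adjusted | Variance ratio | CI narrower by | 50 adjusted patients equal | Detectable difference at 80% power (SD) |
|---|---|---|---|---|---|---|
| 0.3 | 0.335 | 0.270 | 0.65 | 19.4% | 77 | 0.94 → 0.76 |
| 0.5 | 0.283 | 0.245 | 0.75 | 13.4% | 67 | 0.79 → 0.69 |
| 0.7 | 0.219 | 0.202 | 0.85 | 7.8% | 59 | 0.61 → 0.57 |
| 0.9 | 0.126 | 0.123 | 0.95 | 2.5% | 53 | 0.354 → 0.345 |

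Exact generalised least squares gives the same SEs for the SAP model and for a common-D0-mean model, with two periods (TMT) and with five (balance, NPC). In 3,000 simulated trials per setting with five periods, ANCOVA had an SD of 0.2489 against 0.2842 for the SAP contrast at rho 0.5. That is a ratio of (0.2489/0.2842)² = 0.77 rather than 0.75, because the slope must be estimated.

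**Unequal variances.** With SD s0 at D0 and s1 later, the ratio is s1²(1 − rho²) / (s0² + s1² − 2·rho·s0·s1). Denominator minus numerator is (s0 − rho·s1)², so the ratio never exceeds 1 before the small cost of the slope. If s1 = 0.7·s0 it is 0.47, 0.49 and 0.40 at rho 0.5, 0.7 and 0.9. If s1 = 2·s0 and rho = 0.5 it is 4 × 0.75 / (1 + 4 − 2) = 1, so there is no gain.

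**Does the SCAT5 wording help?** A covariate that is constant within a patient cancels from that patient's change while D0 remains in the response. At rho 0.5 with five periods, the simulated SD of the change contrast was 0.2842 both with and without it.

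**Is a common D0 mean safe under a random intercept alone?** In two-period simulations (25 per arm, rho 0.5), its type I error was about 0.004 when the later SD halves and 0.106 to 0.116 when it doubles. The SAP model gave 0.044 and 0.043, and ANCOVA about 0.04.

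**The case against.** The strongest reply is that nothing here is invalid. The SAP contrast is unbiased, holds its type I error and follows the protocol. It concerns secondary endpoints of a pilot with no power calculation, and protocol 9.2.3 already names larger limits: an uncontrolled placebo effect, unblinded investigators and a single site. All of that stands. What remains is that the SAP prints p-values for a comparison meant to inform the choice of frequency, and its precision can be improved from data already collected.

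A second reply is that the template footnote already provides for a baseline covariate. It is an unfilled placeholder, gender is the only covariate the text names, and a D0 value entered there with D0 still in the response would not change the contrast.

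A third is that the remedy has costs. This also stands in part:
- The common-D0-mean model is fragile under the SAP's random-intercept covariance. It also leans on randomisation, while SAP section 5 analyses patients as treated.
- Removing D0 from the response removes the within-arm changes, which are the evolution endpoints of protocol 9.5.4.2.
- SAP 2.0 (03/08/2023) follows a data review of 18/07/2023, so changing a protocol-specified model at that stage has a credibility cost.

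A reader might extend the point to the yes/no cover test and Maddox endpoints. The formula does not cover binary outcomes, and their template reports odds ratios by visit and within arm rather than a between-arm difference in change. Modelling post-D0 visits only would delete the within-arm odds ratios against D0.

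**Conclusion.** The point holds as a loss of efficiency for the continuous endpoints: the balance parameters, NPC analysed as a measurement, and TMT. Under equal variances and complete data, the variance after adjustment is 0.65 to 0.95 of the SAP contrast's for rho from 0.3 to 0.9. The gain is material at low rho and slight at high rho, and unequal variances can enlarge it or remove it.

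The NPC part depends on the scale. SAP 6.2.2 uses the measure, whereas protocol 9.6.3.2 splits it at 5 cm, and SAP section 10 does not list the difference. If the binary form is analysed, (1+rho)/2 does not apply.

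A reader might infer that the planned comparison is biased, or that adjustment is worth a third more patients at no cost. The documents support neither. The contrast is valid, and the second figure is simply 67 against 50 at rho 0.5, a value the documents do not supply. The primary ADE analysis, the descriptive blood markers and the pooled D0-to-D52 analysis are unaffected.

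**What to change.** 1. For the between-arm contrast in SAP 8.5.1.1 (balance, NPC as a measurement) and 8.5.1.2 (TMT), model post-D0 visits only, with the D0-before value and its interaction with visit as covariates beside gender. TMT has one post-D0 visit, so this is plain ANCOVA. Name the covariate in place of `variableyyy`.
2. A longitudinal model with a common D0 mean is an alternative, but only with an unstructured covariance and if few or no patients were treated in the wrong group.
3. Use the same structure for SCAT5 instead of adding its baseline while D0 stays in the response.
4. Keep the existing model for within-arm changes from D0, and leave the binary cover test and Maddox models as they are.
5. List the change in SAP section 10 with its date. If results are already known, report the adjusted analysis as supplementary.

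The cost is SAP wording and some programming, with no new data. The small downside is a departure from the protocol-specified model after a data review.

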9.2.3. Justification of the Clinical Investigation Design

RGnCON is a prospective, comparative, randomized, simple-blinded, monocentric, pilot clinical investigation:

- A **prospective** design has been chosen since no data on the use of RGn550 in sportspeople suffering from acute concussion syndrome were previously collected.
- This investigation is **comparative**. It involves two parallel groups differing in terms of treatment frequency: half of the patients will be treated with 5 Hz, the other half with 10 Hz. This will allow to determine which frequency is optimal for the patient both in terms of safety and performance.
- Patients will be assigned to one of these two groups through **randomization** (1:1 ratio).
- Patients will not be aware of the group they were assigned to (**simple blinded**).
- A **monocentric** design has been chosen because RGnCON is a pilot investigation.

Various methodological aspects will prevent investigation bias:

- The presence of two groups will allow to take into consideration all confounding factors, apart from placebo effect.
- The unpredictable randomization will spread all known and unknown confounding factors (apart from placebo effect) within the two groups, resulting in comparable groups, and will prevent selection bias.

- Patients will be stratified based on gender (male/female) and concussion history (history/no history of concussion within 6 months prior to inclusion) as such parameters are known to influence current concussion symptoms and complications.
- The analysis will be performed in the Full Analysis Set (FAS) population without methods to replace missing data. However, some of the used models take into consideration missing data.

Of note, the following bias will remain present:

- The follow-up bias and evaluation bias since investigators will not be blinded
- The site effect since only one site will be recruited.

Nevertheless, the primary purpose of this investigation is to evaluate, for the first time, the safety of RGn550 in sportspeople suffering from acute concussion syndrome and explore its performance in this population. In case this investigation demonstrates RGn550's safety in this population, further investigation(s), using a double-blinding design versus sham, and involving more sites, will be conducted to demonstrate RGn550's safety and performance.

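### For the continuous endpoints in SAP 8.5.1.1 and 8.5.1.2, a gender main effect drops out of the change-from-D0 contrasts, so they are not adjusted for the stratification factor

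*SAP*

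**What the plan says.** Protocol 9.2.3 sets 1:1 randomisation with strata: "Patients will be stratified based on gender (male/female) and concussion history". The reason given is "as such parameters are known to influence current concussion symptoms and complications". Protocol 9.6.3.2 then puts both stratification variables into the mixed models as covariates.

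SAP 8.5.1.1 compares each later timepoint with D0 before treatment. Its model is described as "logistic model for a categorical parameters and a linear model for continuous parameters) will be used with a patient random effect", with group, period (five levels, D0 before treatment included) and group-by-period as fixed effects. On adjustment it says: "The stratification variable gender (male/female) will be added in the model as covariates". No gender-by-period term is mentioned. Concussion history is left out because too few patients had it. SAP 8.5.1.2 has the same gender sentence for the Trail Making Test, measured at two timepoints, and uses the same continuous template. That template takes D0 before treatment as reference, and its footnote shows a p-value for a baseline covariate.

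SAP 8.5.1.3 reads differently: "The stratification variables and SCAT5 baseline will be added in the model as covariates". SAP section 10 does not list the omission of concussion history and states that nothing else changed from the protocol.

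**The concern.** A reader of the tables will see gender in the footnote and take the changes from D0 as adjusted for it. When D0 is one of the responses, a covariate that is constant over visits moves all of a patient's values by the same amount and so cannot alter a change. Gender could affect the changes only by altering the time course, and that term is absent.

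Two things are at stake. The label may mislead. And if men and women change differently, the model-based standard errors are somewhat too large and any gender imbalance between arms is carried into the 5 Hz versus 10 Hz difference. Protocol 9.2.3 intends that comparison to inform the choice of frequency.

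**Working it through.** **The plan's own figure.** The only power-type figure is for the primary endpoint: "For a sample size of 50 patients, the probability of observing at least one ADE will be 0.87 considering a probability of ADE of 0.04". Check: 1 − 0.96^50 = 0.870, which agrees. Nothing is stated for the mixed models, so standard deviations, gender split and gender effects below are assumptions.

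**Step 1: cancellation.** For patient i at period t, with gender G:

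y(i,t) = period + group + group-by-period + γG(i) + u(i) + e(i,t)

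In y(i,t) − y(i,D0), both γG(i) and the patient effect u(i) disappear. With complete data the group-by-period estimates and their standard errors depend only on within-patient deviations (given a positive estimated patient variance), and G has no part in these. Within-patient degrees of freedom are 50×4 − 8 = 192 for five visits and 50×1 − 2 = 48 for the Trail Making Test, with or without gender.

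**Step 2: numerical check.** Simulated data: 50 patients, 5 visits, 14 patients of one gender (8 vs 6 by arm), patient SD 6, residual SD 5, gender effect 4.

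| Quantity | No gender | Gender main effect |
|---|---|---|
| Change D0 to D52, 5 Hz | −9.576 (SE 1.387) | −9.576 (SE 1.387) |
| Between-arm difference in change | 0.313 (SE 1.961) | 0.313 (SE 1.961) |
| Arm difference at D52 | −1.88 (SE 2.20) | −1.41 (SE 2.09) |

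Over 100 complete data sets the largest discrepancy in a change contrast was 1.4e-13. With 5 of 50 patients missing from D7, the between-arm difference in change moved by a median of 0.028 and at most 0.135, against an SE of about 2.

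**Step 3: where gender does act.** The third row above shows an arm comparison at a visit. In simulated logistic models, a within-arm D52 versus D0 odds ratio moved from 0.2490 to 0.2425, and in another data set the arm odds ratio at D52 moved from 1.67 to 1.95.

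**Step 4: size if gender modifies change.** Let p be the proportion of women and d the gender difference in D0-to-D52 change, in SDs of change (√2 times the residual SD). Let c(t) be the share of that difference present at period t, T the number of periods, and S = Σ(c(t) − mean c)². Leaving out gender-by-period inflates the residual variance by about

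2p(1−p)d² × S/(T−1)

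- Trail Making Test: c = (0, 1), S = 0.5, T−1 = 1, so the inflation is p(1−p)d². At p = 0.5 and d = 0.8 it is 0.25×0.64 = 16%. At p = 0.1 and d = 0.3 it is 0.09×0.09 = 0.8%.
- Five visits, difference at D52 only or at every visit after D0: S = 0.8. At p = 0.5 and d = 0.8: 2×0.25×0.64×0.2 = 6.4%. At p = 0.1 and d = 0.3: 2×0.09×0.09×0.2 = 0.3%.
- Five visits, even build-up: S = 0.625, giving 2×0.25×0.64×0.156 = 5.0% at the upper end.
- A jump at D7 that persists: S = 1.2, giving 9.6%, so the five-visit figure depends on this profile.

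At the upper ends of 16% and 6.4%, standard errors are too large by factors of √1.16 = 1.08 and √1.064 = 1.03.

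**Step 5: imbalance.** The carry-over is the difference in the proportion of women times the gender difference in change. Two extra women in one arm of 25 give 2/25 = 0.08; at d = 0.8 that is 0.064 SD of change. The standard error is √(1/25 + 1/25) = 0.283 SD, so this is about 0.23 of a standard error.

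**Step 6: cost if gender does not modify change.** Assuming blocks of 4 stratified by gender, the precision loss is at most about 0.4%. With the 8 vs 6 split above, the SE in one data set went from 1.961 to 1.977.

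**The case against.** The affected endpoints are secondary and unpowered in a pilot whose primary endpoint is ADE incidence, with no multiplicity control. The protocol called for stratification variables as covariates, and on gender the SAP does what it said. That limits the weight of the point but does not make the adjustment work.

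Three stronger readings are tempting and not supported.

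- *Gender is inert throughout 8.5.1.1.* It is not. The cover test and the Maddox yes/no endpoints use logistic models, the categorical template includes arm odds ratios at a visit, and the continuous template could be read as visit means. Gender affects all of these.
- *The benefit of stratifying is lost.* Balance comes from the randomisation, and a constant gender difference is already removed by taking changes. With gender balanced, omitting gender-by-period causes no bias. In 1,500 simulated balanced sets per scenario, the ratio of true sampling variances with and without the term was 0.999 to 1.010. What changes is the reported standard error.
- *The protocol says that men and women recover at different rates.* It refers to "as such parameters are known to influence current concussion symptoms and complications", and Protocol 9.2.1.1.4 to greater severity in sportswomen. Symptoms and severity are differences in level. Complications may suggest a different course, but no document states one.

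A large imbalance should not be presumed either. A split such as 7 vs 4 women would carry over 3/25 = 0.12 of the gender difference in change, but the documents give neither the split nor the block size. With blocks of 4, an incomplete block leaves a difference of at most 2 within a stratum.

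**Conclusion.** The point holds for the continuous endpoints in SAP 8.5.1.1 and 8.5.1.2. Their change-from-D0 contrasts, and the between-arm difference in those changes, are not adjusted for gender, although the output will list it as a covariate. The cancellation is exact with complete data and close to exact with a few missing visits. Loss to follow-up is reported as 0% in SAP 8.4.1, but Protocol 9.5.5.2 stops performance tests after a second concussion or contraindication.

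The size is modest: variance overstated by roughly 0–6% in the five-visit models and 0–16% for the Trail Making Test. This assumes 10–50% women, a gender difference in change of 0–0.8 SD, and for five visits a difference that builds up evenly, appears only at D52 or is present at all later visits. The case rests on correct labelling, correct standard errors and protection against residual imbalance, not on gaining power.

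The differing treatment of concussion history in 8.5.1.1 and 8.5.1.3 is a minor, separate inconsistency that can be seen from the text alone.

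**What to change.** 1. In SAP 8.5.1.1 and 8.5.1.2, add gender-by-period as a fixed effect for the continuous endpoints, alongside the gender main effect.
2. State that the Difference column is the between-arm difference in change from D0, and that the per-arm rows are changes averaged over the observed gender proportions. Equal weighting of the genders would otherwise shift the within-arm changes if women are a minority.
3. Align the plural on stratification variables in 8.5.1.3 with the decision in 8.5.1.1 to leave out concussion history. List that omission, and the new term, in SAP section 10.

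The cost is one model term and a few sentences. Within-patient degrees of freedom fall from 192 to 188 for five visits and from 48 to 47 for the Trail Making Test. The precision loss is negligible if gender does not modify change. The logistic models need no change on this account.
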